This is a prospective placebo-controlled randomized study. Patients will enter with active disease. After informed consent and screening procedures are completed, enrolled patients may be optionally treated with intramuscular methylprednisolone acetate and background immune-suppressive medications will be withdrawn. Injection of methylprednisolone acetate may be repeated in week 2 at the discretion of the investigator, to induce a state of remission/low disease activity. Patients will be assigned to begin the study medication upon enrollment (baseline, week 0). Patients will be randomized 1:1 to Aggrenox or half of an 81mg aspirin tablet twice daily for 24 weeks. Aggrenox will be initiated at a single bedtime dose for a week, followed by twice daily administration for the rest of the study, to minimize the risk of side effects (e.g. dizziness, headache). Aspirin will be titrated similarly to preserve blinding. Gelatin capsules will be used to cover the pills in order to preserve the blinding.

Participants will be evaluated at baseline (week 0), week 2, week 4 and every 4 weeks until the completion of the study at week 24. An additional study visit may be scheduled at the time of a clinically significant flare (flare visit). Evaluation of general health status, adverse events and lupus disease activity (SLEDAI, BILAG, PGA, CLASI, DIAL, SF-36v2, Lupus QoL, FACIT-fatigue, PSQI, CES-D) will be performed at baseline, week 4 and every subsequent visit. Time to first flare and severity of first flare will be examined. At the time of a clinically significant flare

(defined as at least one BILAG letter grade increase or an increase of ≥ 3 points in SLEDAI AND clinician determination of clinically significant deterioration) patients may elect further treatment with intramuscular methylprednisolone acetate or, if necessary DMARD therapy, but will continue the study as permanent nonresponders.

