Patients will have CBC with differential, metabolic profile, urinalysis, anti-dsDNA, and complement studies performed at baseline, each of the subsequent monthly visits through week 24 and the flare visit. If urine dipstick is $\geq 2+$, a protein/creatinine ratio will be performed at the following visit (or sooner at the discretion of the investigator). Pharmacodynamic and exploratory blood and urine biomarker samples will be drawn prior to first dose at baseline, at weeks 8 or 12, week 24 and at the flare visit. Some of the stimulated cell gene expression and signaling pathway work will be performed on deidentified samples in collaboration with Drs. [name] and [name] at Beth Israel Medical Center in Boston Massachusetts. We will have a material transfer agreement with that institution. In the context of our ancillary study of heart rate variability in lupus, a 5-minute ECG will be performed at each monthly visit and at the flare visit (please see attached protocol).

Summary of Medications and Medication Changes

At screening, participants may be receiving daily prednisone at a dose of 20mg or less, and/or one or more of the following DMARDs: hydroxychloroquine, methotrexate, azathioprine and mycophenolate mofetil, and must be agreeable to discontinue their background immune suppressants upon enrollment. Patients taking hydroxychloroquine upon enrollment will however continue the medication throughout the study.

All participants may be administered optional intramuscular methylprednisolone acetate upon enrollment (usually 160mg, but dose may adjusted based on clinical judgment). Intramuscular steroid treatment may be repeated at weeks 2 at the discretion of the investigator, to induce a state of remission/low disease activity while background medications are withdrawn. Patients on oral steroids will be given an optional rapid taper over 3-4 weeks.

Duration of participation

Participants will receive treatment for a total of 24 weeks.

Patient enrollment

A maximum of 50 patients meeting the inclusion criteria and not meeting the exclusion criteria will be enrolled in the study. The enrollment period is expected to last for at least 18 months but could last as long as four years.

Data collection and analysis

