Data will be collected by study personnel who will be kept blinded to treatment assignments. A trained study coordinator will provide data monitoring and quality assurance checks on the database. The final data will be pooled and analyzed by the investigators.

E. Statistical methods

The primary analysis will be an intention-to-treat two by two table.

Primary endpoint: A two by two table analysis of rate of response by the BICLA response index at week 24 compared to baseline (week 0) in patients on aspirin versus Aggrenox regimens, with non-response attributed to patients who receive defined non-responder treatments and/or withdraw early. Please see below for power calculations based on expected response rates. Independent predictors of BICLA response, including baseline biomarkers, biomarker responses to Aggrenox treatment, demographics and amount of steroids administered, will be further investigated by exploratory logistic regression modeling.

Secondary endpoints: Flare rates at week 24 compared between completers among treatment groups. Time to flare (log rank test). SRI 4/5 at week 24, BICLA and SRI 4/5 at each month. HRQOL comparing treatment groups versus baseline at week 24 and at each month. Although our primary endpoint is based on the BICLA response, an accepted outcome for lupus clinical trials which serves as a pilot response indicator for future trials, it is likely that some secondary endpoints, such as time to flare will be more sensitive, and more likely to achieve significance in a pilot study.

Exploratory endpoints: SRI component analyses and CLASI responses. Refinement in BICLA and SRI analysis using a propensity score derived by multiple potential confounders identified in exploratory single variate analysis. Relation of clinical and biologic endpoints with heart rate variability measures by multivariate analysis.

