Biologic Endpoints: Changes in B cell and T cell subsets, relevant gene expression patterns, B-T cytokine profiles and cell-bound complement split products and urinary biomarkers at baseline versus week 24 in each treatment group. Evaluation of B Cell/T cell expression patterns in patients with higher versus lower IL6, IL17 and IL23 expression detected at baseline. These endpoints will be evaluated both as changes with Aggrenox versus aspirin treatment (non parametric analysis) and as components of multivariate modeling and propensity score analysis as described above. An exploratory responder analysis will also be performed (changes in these biomarkers with response versus non-response in patients receiving Aggrenox). The latter analysis may need to be observational only, as it is likely to be underpowered and diluted by patients who may not have begun the trial with the characteristic abnormalities in T cell subset activity.

Power/Sample size calculation

We base this calculation on preliminary data from the BOLD study (11) which is an exploration of underlying biology in patients with SLE who receive steroids and are withdrawn from background treatments, in other words identical to the aspirin group in the current proposal. To date we have analyzed data from 31 patients who completed the BOLD protocol and these outcomes suggest that no more than 20% of the aspirin group will achieve a BICLA response at week 16 (range 1-20%) and no more than 5% achieves a BICLA response at week 24 (range 0-10%). Assuming a 35 to 50% response rate in the Aggrenox group at week 24, a sample size of 50 patients will provide a power around 80% at a significance level of 0.05 at week 24. By these settings and assumptions, the following power estimates are obtained.

Power calculations for a 50 patient study, if alpha=0.05 with response rates:

	Rate 1	Rate 2	Rate 3	Rate 4	Rate 5	Rate 6	Rate 7
Aggrenox n=25	60%	55%	50%	45%	40%	35%	35%
Aspirin n=25	20%	15%	10%	10%	5%	5%	3%
power	0.84	0.86	0.89	0.80	0.86	0.77	0.84

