An absolute difference of ≥ 12 to 15% in the response rate is however considered clinically significant in other lupus trials. Since this is a pilot study, a clinically significant (12% or greater absolute difference), but not statistically significant difference, might be considered justification for a larger study. Even if this pilot study does not reach statistical significance, the proposed exploratory biomarker studies evaluating T and B cell phenotypes, T/B cell functional studies, gene expression or serum cytokine/chemokine profiles might be used to refine the entry criteria and biologic treatment goals for a further study and/or underscore the rationale for an expansion of this study for more power of discrimination. Finally, the BICLA and other flare analyses will be performed at each monthly visit, increasing the likelihood of finding differences, should they exist, when including these secondary analyses.

An interim analysis will be performed after 20 patients will have completed the study, and will be used to assess the quality of the data collected and the treatment effects. Consideration of sample size changes can be discussed at that time.

F. Gender/Minority/Pediatric Inclusion for Research

Participants will be age 18 or older. Race, minority status and gender will not affect enrollment.

G. Human participants

The study population will include male/female patients with SLE, of age 18 or older and of all races.

Inclusion Criteria:

1. Patients with SLE meeting the ACR Classification Criteria (19)
2. Males or females, age 18-70
3. Evidence of positive ANA or anti-dsDNA within one year of screening
4. SLEDAI ≥ 4 or ≥ 1 BILAG B or A at screening, despite standard of care

Exclusion Criteria

1. WBC $< 2,000/\text{mm}^3$, lymphocytes $< 300/\text{mm}^3$ (last known labs)
2. AST or ALT > 3 times above normal cut off values (last known labs)
3. Acute lupus nephritis defined as class II, III, IV or V nephritis diagnosed within 6 months or prot/creat > 1.5 gm/gm due to active lupus or in process of receiving induction therapy for nephritis
4. Active CNS lupus affecting mental status
5. Pregnancy or breast feeding
6. Current requirement for anticoagulation
7. Contraindication to aspirin or dipyridamole, including history of recent or severe GI bleeding, hemoglobin < 9 mg/dL, platelet count of $< 30,000/\text{mm}^3$ or unstable platelet count (last known labs)

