We will modify the DARE protocol as following: The randomized controlled part of the study (group A) will be temporarily interrupted in order to focus our work on the pharmacology of Aggrenox. Patients enrolled will be assigned to open label Aggrenox for 3 months (group B) using the same protocol as in the randomized controlled study. There will be no control arm in this modified phase. We plan to enroll in group B 10 more patients with mild to moderate disease, using the same inclusion and exclusion criteria as in the parent study (group A). However, only patients with a Th17 signature, defined by serum cytokine and gene expression profiling, will be invited to participate in group B. Patients will be instructed to hold their background medications as in the parent study, and will not be allowed to receive any additional steroids. Patients who flare during this study or who have persistently active disease, may elect to be treated with steroids and other immune suppressants as needed, but will be nonresponders for the primary endpoint at 3 months.

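### Grouping baseline IL6, IL17 and IL23 as higher or lower, with no cut-point stated, costs one exploratory biomarker evaluation information if the relation is roughly linear

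*Combined protocol and SAP*

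**What the plan says.** Section E (Statistical methods), *Biologic Endpoints*, includes this item: "Evaluation of B Cell/T cell expression patterns in patients with higher versus lower IL6, IL17 and IL23 expression detected at baseline". It describes a two-group comparison on each of three measured quantities. The documents do not say whether the boundary is a median, a laboratory reference limit or something chosen from the data, and they give no group sizes, scale or test.

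Other parts of section E bear on it:

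- The next sentence adds further analyses of the biologic endpoints: "These endpoints will be evaluated both as changes with Aggrenox versus aspirin treatment (non parametric analysis) and as components of multivariate modeling". It does not say in what form the cytokines enter those models.
- *Primary endpoint* lists candidate predictors for an exploratory logistic regression: "Independent predictors of BICLA response, including baseline biomarkers, biomarker responses to Aggrenox treatment, demographics and amount of steroids administered". No splitting is mentioned, but neither is a continuous form.
- *Power/Sample size calculation* says the exploratory biomarker work "might be used to refine the entry criteria and biologic treatment goals for a further study".

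On size, section D (*Patient enrollment*) states: "A maximum of 50 patients meeting the inclusion criteria and not meeting the exclusion criteria will be enrolled in the study". The amendment of January 13, 2015 then temporarily interrupts the randomized part and opens an uncontrolled group B, in which "only patients with a Th17 signature, defined by serum cytokine and gene expression profiling, will be invited to participate in group B". It gives no numeric threshold for that signature.

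**The concern.** A two-group comparison treats a patient just above the boundary like the patient with the highest value, and unlike the patient just below it. When the outcome changes steadily with the marker, that discards real differences between patients, and a study of at most 50 has few to spare.

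An unstated boundary adds a second problem. If it is chosen after the expression data have been seen, the nominal significance level no longer holds. The choice can also be made separately for each of three cytokines.

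What is at stake is how reliably this evaluation can link the cytokines to T and B cell patterns. The plan hopes that biomarker results of this kind will shape a later study's entry criteria.

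**Working it through.** **Inputs from the documents.** At most 50 patients; 1:1 allocation, so 25 per arm; alpha 0.05. The sidedness of the test is not stated.

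**The plan's own figure.** The only power figures are the seven in the BICLA table. A two-sided, pooled-variance comparison of two proportions without continuity correction reproduces them. For 60% v 20%:

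- critical difference = 1.96 × sqrt(2 × 0.40 × 0.60 / 25) = 0.2716
- standard error under the alternative = sqrt((0.24 + 0.16) / 25) = 0.1265
- power = Phi((0.40 − 0.2716) / 0.1265) = Phi(1.015) = 0.845 (plan: 0.84)

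The seven results are 0.845, 0.866, 0.895, 0.811, 0.865, 0.772 and 0.844, against 0.84, 0.86, 0.89, 0.80, 0.86, 0.77 and 0.84. This supports reading alpha as two-sided. The table says nothing about the cytokine evaluation, for which the documents give no power or precision.

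**Assumptions, none of them in the documents.** One cytokine against one expression measure, a linear relation, a normal marker (for example after a log transform) unless stated otherwise, and complete data.

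**Information kept by a split.** This is the squared correlation between the marker and its high/low indicator. For a normal marker cut at quantile q it equals phi(z_q)² / [q(1 − q)].

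| Marker and cut | Calculation | Kept | Lost |
|---|---|---|---|
| Normal, median | 0.3989² / 0.25 = 2/pi | 0.637 | 36% |
| Normal, 60/40 | 0.3863² / 0.24 | 0.622 | 38% |
| Normal, 75/25 | 0.3178² / 0.1875 | 0.539 | 46% |
| Normal, 90/10 | 0.1755² / 0.09 | 0.342 | 66% |
| Uniform, median | (1/8)² / [(1/12)(1/4)] | 0.750 | 25% |

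For the normal marker cut at the median, 50 × 0.637 = 31.8, so 50 patients inform this comparison about as well as 32 would with the marker kept continuous.

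**Power.** By Fisher's z with n = 50 and rho = 0.4:

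- continuous: Phi(arctanh(0.4) × sqrt(47) − 1.96) = Phi(2.904 − 1.96) = 0.83
- median split: rho shrinks to 0.4 × sqrt(0.637) = 0.319, giving Phi(2.267 − 1.96) = 0.62

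Simulation from bivariate normal data (two-sided 0.05; results vary by a point or two between runs) agrees:

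| n | rho | Pearson | Median split |
|---|---|---|---|
| 50 | 0.3 | 0.57 | 0.40 |
| 50 | 0.4 | 0.84 | 0.64 |
| 50 | 0.5 | 0.97 | 0.84 |
| 25 | 0.4 | 0.52 | 0.34 |
| 25 | 0.5 | 0.75 | 0.52 |

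At rho = 0.4, Spearman gives 0.79 for n = 50 and 0.47 for n = 25. A 75/25 split with n = 50 gives 0.54.

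**Open cut-point.** Simulated with no association, n = 50, one cytokine and one expression measure: taking the best of three cuts (one third, median, two thirds) raises the false-positive rate from 5% to about 11%. Searching every cut between the 20th and 80th percentiles raises it to about 28%.

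**Non-linear check.** With a step of 0.8 SD exactly at the population median and n = 50, power is about 0.57 for Pearson, 0.61 for Spearman and 0.67 for the median split. Here the split does better.

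**The case against.** The strongest reply is that the size of the loss does not come from the plan. No median cut, distribution or form of relation is stated, and 64% is specific to a normal marker, a median cut and a linear relation. That stands, so the figure must be given as conditional and with a range. It also does not extend to monotone relations in general, as the step example shows. A threshold relation is plausible here, because the plan itself worries about patients who entered without the characteristic T cell abnormality.

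A second reply is that the plan also puts biomarkers into logistic and multivariate models. This stands in part: the documents do not show that continuous information is discarded everywhere. But those models do not state how the cytokines enter, and the logistic model predicts BICLA response, not expression patterns. Neither replaces the higher/lower comparison.

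A third reply is that later entry criteria need a class, and group B did select patients by a Th17 signature. That is a reason to set a threshold in advance, not to make an unspecified split the main test of association. The documents do not say that this evaluation produced the group B criterion.

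A reader might also infer that the study as a whole gives up a third of its information, as if 18 of its 50 patients were dropped (50 × 0.363 = 18). The documents do not support that. The split belongs to one exploratory biologic evaluation, and the 18 needs the same unstated assumptions as the 64%.

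**Conclusion.** The point holds for this one evaluation. The plan describes a two-group comparison of quantitative markers without a cut-point, and a continuous analysis is more powerful when the relation is roughly linear. Under linearity, the cases computed lose from 25% (uniform marker, median cut) to 66% (normal marker, 90/10 cut), with 36% for a normal marker cut at its median. At n = 50 and rho = 0.4, this means power of about 0.84 (Pearson) or 0.79 (Spearman) against about 0.64 with a median split. The correlations are illustrative. Because 50 is a maximum and the randomized part was interrupted, the number with data may be smaller.

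The unfixed cut-point is a separate weakness that does not depend on linearity. Importance is low: the evaluation is exploratory, and no primary or secondary clinical analysis uses the split.

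**What to change.** In *Biologic Endpoints*, state that the main analysis of each baseline cytokine (IL6, IL17, IL23) against each expression measure treats the cytokine as continuous, by regression on the log scale or by Spearman rank correlation, and name which. Keep any higher/lower grouping as a secondary or descriptive display, at a cut-point and by a rule written down before the expression data are seen. If a class is wanted for a later study's entry criteria, set its threshold separately and in advance; the continuous analysis does not supply one.

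The cost is a few sentences, with no extra patients, samples or assays. The one downside is a slight loss of power if the true relation is a sharp step near the chosen cut (about 0.57 to 0.61 against 0.67 in the example above). The pre-set grouped display would still let such a step be seen.

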The enhanced calcium/calcineurin/NF-AT pathway in human and murine SLE T cells can be suppressed in presence of dipyridamole (7). Dipyridamole abrogates expression of costimulatory molecules and production of cytokines by SLE T cells and inhibits T cell directed B cell antibody production. Administration of dipyridamole to MRL/lpr mice inhibits production of IL6 and delays the emergence of lupus related pathology, including nephritis and skin disease. Taken together, these observations justify a clinical study of dipyridamole in patients with SLE.

C. Preliminary studies

There is an ongoing need for new treatments in SLE that will target specific immune pathways and provide immunomodulation with limited immunosuppression and acceptable tolerance. Recent clinical trials of new medications for treatment of SLE have however been hampered by disease heterogeneity and confounded by background medications, as well as the use of various, inadequately validated measures of disease activity (8).

Recent genetic and mechanistic studies in SLE provide valuable insight into disease heterogeneity, and biomarkers of disease activity (9). A gene expression array of genes contributing to aberrant T cell function was recently found useful in SLE diagnosis and classification (10). Similar arrays may be also useful for monitoring of T cell targeted therapies.

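### Read literally, the plan puts baseline-to-week-24 biomarker changes into the propensity score for BICLA and SRI, and nothing limits that score to pre-dose variables

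*Combined protocol and SAP*

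**What the plan says.** The relevant text is in section E, Statistical methods.

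- **Biologic Endpoints.** The listed endpoints are changes in cell subsets, gene expression, cytokines, complement split products and "urinary biomarkers at baseline versus week 24 in each treatment group". A further item concerns patients grouped by baseline IL6, IL17 and IL23. The endpoints have two stated uses: as changes compared between arms, and "as components of multivariate modeling and propensity score analysis as described above".
- **Exploratory endpoints.** The only propensity score described above that paragraph is this one: "Refinement in BICLA and SRI analysis using a propensity score derived by multiple potential confounders identified in exploratory single variate analysis".
- **Primary endpoint.** An exploratory logistic model looks for predictors of BICLA response, "including baseline biomarkers, biomarker responses to Aggrenox treatment, demographics" and amount of steroids. It names baseline and on-treatment biomarkers side by side.

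Three passages elsewhere bear on the point. Section D states "Patients will be randomized 1:1 to Aggrenox" (the comparator is aspirin) and says biomarker samples are "drawn prior to first dose at baseline, at weeks 8 or 12, week 24 and at the flare visit". Section B describes the proposed mechanism: "Dipyridamole abrogates expression of costimulatory molecules and production of cytokines by SLE T cells". No section, including the January 2015 amendment, says that the score uses only pre-dose variables.

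**The concern.** Treatment is assigned at random, so a biomarker change that occurs after dosing cannot confound assignment. It can be a consequence of assignment. Section B places T-cell cytokines and costimulation on the drug's proposed pathway, so several of the listed changes are candidate mediators of response.

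A score containing such changes does two unwanted things:

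- It removes the part of the drug effect that runs through the biomarker, which usually pulls the estimate towards zero.
- If the biomarker and response share unmeasured causes, it opens a non-causal path and can bias the estimate in either direction.

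The adjusted BICLA/SRI comparison would then answer a different question from the unadjusted comparison it is meant to refine. Choosing covariates by single-variate screening gives no protection. Whether the screen is run against arm or against response, it can select a marker that the drug moves.

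**Working it through.** **Plan's own figure.** The concern rests on no stated number. The nearest is the power table, from which the illustration takes the pair 40% v 5% with 25 per arm. The pooled two-sided normal approximation gives:

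- mean rate (0.40 + 0.05)/2 = 0.225
- null SE √(2 × 0.225 × 0.775/25) = 0.1181; times 1.96 = 0.2315
- alternative SE √((0.40 × 0.60 + 0.05 × 0.95)/25) = 0.1072
- power = Φ((0.35 − 0.2315)/0.1072) = Φ(1.105) = 0.865, against the stated 0.86

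The other six columns also reproduce, to within about 1 point. The table neither supports nor contradicts the concern; it supplies a true difference of 35 points.

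**Assumptions (not in the documents).** There is one on-treatment biomarker M with SD 1, mean 0 on aspirin and mean δ on Aggrenox, with δ in the favourable direction. The logit of response is a(arm) + βM, with a(arm) solved so that the marginal rates are 40% and 5%. Data are complete and allocation is 1:1.

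**Formula.** The score is a logistic regression of arm on M. Weighting by its inverse gives both arms the pooled distribution of M, an equal mixture of N(0,1) and N(δ,1). So

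adjusted difference = E_pooled[p(Aggrenox, M)] − E_pooled[p(aspirin, M)].

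**One case in full, β = 1, δ = 1.** The solved intercepts are −1.490 (Aggrenox) and −3.372 (aspirin).

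- Aggrenox: 40.0% at its own M distribution and 22.3% at the aspirin distribution; average about 31.1%.
- Aspirin: 5.0% at its own M distribution and 11.7% at the Aggrenox distribution; average about 8.3%.
- Adjusted difference: about 22.8 points instead of 35.

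**All cases (points, by numerical integration):**

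| Log-odds per SD (β) | δ = 0.5 | δ = 1.0 | δ = 1.5 |
|---|---|---|---|
| 0 | 35.0 | 35.0 | 35.0 |
| 0.5 | 31.6 | 28.2 | 24.9 |
| 1.0 | 28.9 | 22.8 | 16.8 |
| 1.5 | 27.0 | 19.0 | 10.9 |

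A simulation with 1,000,000 patients agrees within 0.2 points. Linear regression on arm plus score agrees with weighting within 0.6 points.

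**Comparator: score from one pre-dose variable.** In 5,000 simulated trials at 25 per arm, with the same β of 0.5, 1.0 and 1.5, the mean adjusted difference was 35.1, 35.0 and 35.1 points. The adjustment moved a single trial's estimate only by chance (SD 2.5, 3.8 and 4.7 points).

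**A second model, indexed by share of effect mediated.** At shifts of 1.0 to 1.5 SD the large-sample adjusted difference was about 35 points if the biomarker carries none of the effect and about 18 if it carries half on the logit scale. It was about 0 if the biomarker carries all of the effect (1.5 SD). At 50 patients the corresponding means were about 35, 19 to 20, and 6 points. The SD of the estimate rose from about 11 points to 12 to 16.

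**Direction check.** The drug was given no effect on response (5% in both arms), a biomarker shift of 0.5 or 1 SD up or down, and an unmeasured cause correlated 0.3 or 0.7 with the biomarker, with log-odds 1 or 2 on response. The spurious difference was 0.7 to 5.6 points, with its sign set by the direction of the shift.

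**The case against.** The strongest reply is that the text need not mean this.

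- **Grammar.** Form is attached only to the first use, the between-arm comparison of changes. The form in which biomarkers enter the second use is not given, and the preceding sentence concerns cytokines at baseline.
- **The word confounders.** The score is built from potential confounders, and a post-dose change cannot be one.
- **Role.** These variables are called endpoints, so they could be the outcomes of adjusted models, as in the planned heart-rate-variability analysis. The changes could also be meant only for the predictor regression, which already names biomarker responses.
- **Feasibility.** A week-24 change makes little sense as a covariate for the monthly BICLA and SRI analyses. It may also be missing for early withdrawals, who count as nonresponders.
- **Purpose.** Conditioning on biomarker change is legitimate for a mechanistic question, and the plan never says the refined result is the total drug effect.
- **Size.** Every biomarker input is assumed, the 11-point figure combines the two most extreme inputs, and about one aspirin responder is expected (5% of 25). The estimate is imprecise either way.

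Much of this stands. The text is ambiguous, the numbers are illustrative, and no decision rule is tied to the score: section E mentions a 12-point difference as possible grounds for a larger study but does not refer to an adjusted difference. It does not remove the point. A baseline-only convention cannot be presumed when the predictor model openly mixes baseline and on-treatment biomarkers. The feasibility arguments show that the literal reading would work badly, not that the plan excludes it.

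**Conclusion.** The concern holds as a minor point, with medium confidence that the literal reading is the one intended. Following it would make the adjusted BICLA/SRI comparison something other than the total drug effect. Under the assumed single-biomarker model, a true 35-point difference would appear as about 11 to 32 points when the biomarker affects response, and as 35 when it does not. Several biomarkers in one score, and missing week-24 samples, are not represented in that range.

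The consequence is confined to an exploratory analysis of the randomised part (group A). The primary intention-to-treat two-by-two table and its power are unaffected. The amendment interrupts group A temporarily, and the point does not arise in group B: "There will be no control arm in this modified phase".

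**What to change.** In section E, under both Exploratory endpoints and Biologic Endpoints, state that the propensity score, and any adjusted model for the treatment effect on BICLA or SRI, uses only variables measured before first dose. Report the week-24 biomarker changes separately: as outcomes compared by arm, and as descriptive associations with response, including the Aggrenox-arm responder analysis already planned.

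The cost is wording only, because pre-dose biomarker samples are already scheduled. The one thing given up is that biomarker changes no longer enter the refined estimate of the drug effect. If baseline variables were always intended, the sentence changes nothing.
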